- actual and change from baseline in fasting glucose (average of measurements at time -15 and 0), and PPG at 15, 30, 60, 120, 180, and 240 minutes after the meal
- PPG excursions at time 15, 30, 180, and 240 minutes after the meal (PPG minus fasting glucose)

Sensitivity analysis for PPG and excursions may be performed to exclude patients whose PPG and excursion could be affected by factors including MMTT consumption amount (for example, partial MMTT was consumed).

Treatment comparisons for the proportion of patients with HbA1c $< 7.0\%$ and $\leq 6.5\%$ will be analyzed using a longitudinal logistic regression with repeated measurements conducted by a generalized linear mixed model including independent variables of treatment, baseline HbA1c value, visit, baseline HbA1c-by-visit interaction, and treatment-by-visit interaction. An unstructured covariance structure will be used.

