Efficacy Endpoint: Incremental AUCs (iAUCs) (after the start of meals)					
	iAUC _{0-1hr}				X
	iAUC _{0-2hr}				X
	iAUC _{0-3hr}				X
	iAUC _{0-4hr}				X
Efficacy Endpoint: Mean Glucose Excursions (after the start of meals) ^d					
	mean sensor glucose excursions 0 to 1 hour				X
	mean sensor glucose excursions 0 to 2 hour				X
	mean sensor glucose excursions 0 to 3 hour				X
	mean sensor glucose excursions 0 to 4 hour				X
Efficacy Endpoint: Hyperglycemic Episodes					
	Duration (in minutes) and percentage of time with glucose values >180, 181-250 and >250 mg/dL [10.0, 10.1-13.9 and 13.9 mmol/L] and hyperglycemic episodes, defined as at least 10 consecutive minutes >180, 181-250 and >250 mg/dL [10.0, 10.1-13.9 and 13.9 mmol/L]	X	X	X	
	Rate (events/patient/year) and incidence (percent of patients with at least 1 event) of hyperglycemic episodes, defined as at least 10 consecutive minutes >180, 181-250 and >250 mg/dL [10.0, 10.1-13.9 and 13.9 mmol/L]	X	X	X	
Efficacy Endpoint: Daily CGM Data Summary					
	Area under the curve (AUC)	X	X	X	
	Mean sensor glucose	X	X	X	
	Median sensor glucose	X	X	X	
	Hourly mean sensor glucose	X			

Category	Endpoints	24-Hour	Daytime ^a	Nighttime ^b	By Meal ^c
	Hourly median sensor glucose	X			
Efficacy Endpoint: Glucose Variability and Risk Assessment					
Within-Day	CV	X	X	X	X
	SD	X	X	X	X
	IQR	X	X	X	X
	MAGE	X	X		X
	LBGI: frequency and extent of low BG readings	X	X		X
	HBGI: frequency and extent of high BG readings	X	X		X
	BGRI = LBGI + HBGI: a measure of overall variability and risks of hypo- and hyperglycemia	X	X		X
Between-Day	CV	X	X	X	
	SD	X	X	X	
	MODD	X	X	X	
Overall ^e	CV	X	X	X	
	SD	X	X	X	
	IQR	X	X	X	
	LBGI	X	X	X	
	HBGI	X	X	X	
	BGRI	X	X	X	
Efficacy Endpoint: Premeal Glucose					
	Premeal Glucose				X
Efficacy Endpoint: Highest Postprandial Glucose					
	Time from start of meal to the highest postprandial glucose level (minutes) within 4 hours after meal(s)				X
	Highest postprandial glucose level within 4 hours after meal(s)				X
	Highest postprandial glucose excursion within 4 hours after meal(s)				X
Safety Endpoint: Hypoglycemic Episodes ^f					
	Duration (in minutes) and percentage of time with sensor glucose values <54, 54-69 and <70 mg/dL of hypoglycemic episodes, defined as at least 10 consecutive minutes <54, 54-69 and <70 mg/dL [3.0, 3.0-3.8 and 3.9 mmol/L]	X	X	X	X

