Appendix 2. Derivation of CGM Variables

General Derivation Specifications

All CGM variables will be derived for each patient, for each valid CGM day and also overall for baseline, Visit 10 (Week 6-8) and Visit 13 (Week 14-16).

No missing CGM values will be imputed.

Since the CGM values may not be measured at the exact same time for each day for a specific individual patient, due to device changes or gaps in usage, non-overlapping intervals ('buckets') of 5 minutes over 00:00:00 to 23:59:59 (00:00:00 to 00:04:59, 00:05:00 to 00:09:59, etc.) will be used for any derivations requiring time-matched measurements across days within a visit (e.g., mean of daily difference [MODD]).

All CGM glucose derivations will be conducted in units of mg/dL and will be converted to mmol/L by multiplying by 0.0555.

Only readings from valid CGM days (defined in Section 6.13) collected between first dose and last dose of study drug (i.e., open-label Humalog used during the lead-in period or IP used during the treatment period) will be included in derivations, excluding data (if any) that are collected while patients temporarily are off pump or off study treatment.

The between-day variability, overall variability, and duration of hypoglycemia episode will be derived using all data collected across all valid CGM days, regardless of CGM days. For the other CGM variables, first determine the values within each day, then average across days within a visit.

The postprandial excursion related CGM variables (e.g., highest postprandial excursions, iAUC and mean sensor glucose) will be derived based upon the same excursion data.

Glucose in Target Ranges, Hypoglycemia- or Hyperglycemia

The percentage of time within a glucose range (target, hypo- or hyperglycemia ranges) will be calculated as the number of observations within the specified range divided by the number of observations in the time interval (e.g., 24-hour period). The duration (in minutes) within the glucose range will then be calculated as the percentage of time within the glucose range times the length of the period (24 hours, 18 hours, and 6 hours, for the periods of 24-hour, daytime or nighttime, respectively).

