where A_i is area of the respective trapezoid, G_i is glucose concentration at a particular time, G₀ is the starting glucose concentration before the start of the meal, Δt_i is the time interval between consecutive CGM values, which should be always 5 minutes unless missing data occur, and k is the total number of intervals within the time frame 0-T, and T could be 1 hr, 2 hr, 3 hr or 4 hr. If the intermediate time points are missing, the next available time point will be used in calculating the trapezoid area. Also since it is possible that G_i < G₀ or G_{i-1} < G₀, A_i could also be negative. G₀, the starting glucose concentration, will be calculated as the average of the CGM values in the time window [-19, 0] mins relative to the start of the meal (at most 3 CGM values); G_k, the last glucose concentration, is defined as the average of the CGM values in the window [0, +14] minutes relative to the last time point of the time frame (at most 2 CGM values). For example, to calculate iAUC_{0-2hr} after the start of breakfast, G_k will be the average of the CGM values in the window [0, +14] minutes relative to the 2 hours after the start of breakfast. The derivation of each iAUC_{0-T} will require that G₀ and G_k values are both available. The derivation iAUC_{0-T} on a specific infusion set wear day, requires that time 0 and time T fall on the same infusion set wear day but allows that the CGM measures in the window [-19,0] for G0 and [0+14] for GT fall on the previous or the next infusion set wear day.

Mean Sensor Glucose Excursions

Mean sensor glucose excursions in a postmeal time interval will be calculated by averaging all excursion values within the time interval where excursions are defined as G_i - G₀ as defined in iAUC.

Hypoglycemic/Hyperglycemic Episodes

Hypoglycemic/hyperglycemic episodes as measured by CGM data are defined as at least 10 consecutive minutes below/above the specified threshold, and determined by 3 or more consecutive CGM values meeting the criterion.

The number of distinct hypoglycemic episodes that start will be derived along with days of CGM use (Section 6.13) to calculate the rate of hypoglycemic episodes during a 24-hour period. For example, the rate of postprandial hypoglycemic episodes (<70 mg/dL [3.9 mmol/L]), during the 24-hour period, will be calculated with the following steps:

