This transforms the BG data using a nonlinear transformation that maps the BG range of 20 to 600 mg/dL to a symmetric interval of $(-\sqrt{10}, \sqrt{10})$

The center of the BG scale is 112.5 mg/dL and is mapped to 0

Step 2: Compute BG risk for each reading

$$rl(BG_i) = 10 \times f(BG_i)^2 \text{ if } f(BG_i) < 0; \text{ otherwise } rl(BG_i) = 0$$

$$rh(BG_i) = 10 \times f(BG_i)^2 \text{ if } f(BG_i) > 0; \text{ otherwise } rh(BG_i) = 0$$

Assign the risk of each BG value by applying the above quadratic risk function

Value range from 0 (achieved when BG = 112.5, the center) to 100

Left side of the parabola is risk of hypoglycemia, and the right side is risk of hyperglycemia

Step 3: Compute LBGI and HBGI

$$LBGI = \frac{1}{n} \sum_{i=1}^n rl(BG_i)$$

$$HBGI = \frac{1}{n} \sum_{i=1}^n rh(BG_i)$$

Step 4: Compute BGRI

$$BGRI = LBGI + HBGI$$

Daily CGM Data Summary

For daily CGM summary variables (Section 6.13), first determine the values within each day, then average across days within a visit. The hourly mean glucose will be calculated as the mean across all CGM values collected, based on actual local time for the subject.

AUC

Area under the curve (AUC) during a period (24-hour, daytime, or nighttime) will be calculated using the standard linear trapezoidal method as defined previously (see section “Incremental Area under the Glucose Curve [iAUC]”) by multiplying the sum of trapezoids by (the length of the period)/ sum of time intervals calculated in the AUC).

Highest Postprandial Glucose

Time from start of meal to the highest postprandial glucose level will be calculated as the time from start of meal to the maximum glucose value within 4 hours after meals, excluding the data from patients who have had the next meal event. If there are multiple time points with the maximum glucose value, then the earliest time will be used.

Highest postprandial glucose level excursions within 4 hours after meals, will be calculated as the maximum glucose value during 0 to 4 hours after start of meal, truncating the data at the next meal event.

Other

The duration of each episode of hypoglycemia will be calculated as stop time – start time.

Leo Document ID = da7d3bbf-504d-42db-90d6-967d07a24b0e

Approver: PPD

Approval Date & Time: 22-Jan-2020 19:08:35 GMT

Signature meaning: Approved

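### SAP Appendix 2 merges the highest postprandial level and the highest excursion into one sentence without the premeal subtraction, which conflicts with Table ITRO 6.5 and the SAP's own definition of an excursion

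*SAP*

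**What the plan says.** In SAP Section 6.13, Table ITRO 6.5 has two separate rows for the size of the postprandial peak, both by meal: "Highest postprandial glucose level within 4 hours after meal(s" and "Highest postprandial glucose excursion within 4 hours after meal(s" (each quote stops just before the closing bracket).

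The Highest Postprandial Glucose part of Appendix 2 gives one rule for the time to the peak and one for its size. The size rule reads: "Highest postprandial glucose level excursions within 4 hours after meals, will be calculated as the maximum glucose value" over the 0 to 4 hours from the start of the meal, with data cut off at the next meal event. No premeal value is subtracted.

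Two other parts of Appendix 2 bear on the same variable:

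- The General Derivation Specifications name it: "The postprandial excursion related CGM variables (e.g., highest postprandial excursions, iAUC and mean sensor glucose) will be derived based upon the same excursion data".
- The part on mean sensor glucose excursions says what excursion data are: "where excursions are defined as G_i - G₀ as defined in iAUC". The iAUC part supplies G0, which "will be calculated as the average of the CGM values in the time window [-19, 0] mins" relative to the start of the meal.

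The rest of the SAP uses the word in the same way. For the mixed meal test, Section 6.11.4 lists "PPG excursions at time 15, 30, 180, and 240 minutes after the meal (PPG minus fasting glucose" (again without its closing bracket). Footnote d to Table ITRO 6.5 subtracts the glucose at meal start for the mean excursions.

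**The concern.** A programmer deriving the highest excursion would naturally go to the subsection on the highest postprandial glucose. That subsection, followed to the letter, returns the peak glucose. The two rows of Table ITRO 6.5 would then hold the same number for every meal, and the row labelled excursion would not measure a rise from the premeal value.

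An arm that merely starts its meals at a lower glucose would then appear to have a smaller excursion. A premeal difference is plausible here. The rationale for amendment (c), in Protocol Appendix 6, cites improvement in both fasting and postprandial glucose in an earlier study and in PK/PD modelling. SAP Table ITRO 6.5 also makes premeal glucose an endpoint.

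**Working it through.** The plan gives no figure to reproduce. The check compares the two rules that Appendix 2 supplies for one variable.

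**Inputs.** G_i is a CGM reading in the 0 to 4 hours after meal start, truncated at the next meal event. G0 is the average of the CGM readings from 19 minutes before meal start up to meal start.

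**Rule A, Highest Postprandial Glucose subsection, read literally.** Excursion = max(G_i). This is also the natural definition of the highest level, so excursion = level.

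**Rule B, General Derivation Specifications with the excursion definition.** Excursion = max(G_i - G0). G0 is constant within a meal, so this equals max(G_i) - G0, which is level - G0.

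**One meal, with assumed values.** Take a peak of 210 mg/dL and three premeal values:

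| G0 (mg/dL) | Level | Excursion, rule A | Excursion, rule B |
|---|---|---|---|
| 80 | 210 | 210 | 210 - 80 = 130 |
| 120 | 210 | 210 | 210 - 120 = 90 |
| 180 | 210 | 210 | 210 - 180 = 30 |

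Rule A cannot distinguish the three meals. Rule B can.

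**Between arms.** Averaging is linear. Over the same set of meals, mean excursion under rule B = mean level - mean G0. Write D_L for the LY900014 minus Humalog difference in mean level and D_0 for the difference in mean G0. Then:

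- rule A reports D_L as the excursion difference;
- rule B reports D_L - D_0;
- rule A minus rule B = D_0.

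The whole premeal difference therefore passes into the rule A result. With D_0 assumed to be -5 mg/dL, rule A shows LY900014 as 5 mg/dL better on excursion than rule B does. With D_0 = -10 mg/dL the gap is 10 mg/dL. With D_0 = 0 the two rules give the same treatment difference.

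**Does the model remove it?** Section 6.13 analyses continuous CGM variables with an MMRM similar to that of the primary endpoint, whose covariate is the baseline-visit value. That is not the premeal glucose of the same post-baseline meals, so the adjustment does not clearly remove D_0. The one-for-one size is exact only for unadjusted means.

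**The case against.** The strongest reply is that the SAP already contains the right rule. The General Derivation Specifications name highest postprandial excursions and tie them to the iAUC excursion data, and those data are G_i - G0. On that view the faulty sentence is a level definition with a stray word, and a careful programmer would subtract G0. The reply adds that the mean excursions and the iAUCs all subtract G0, that premeal glucose is reported alongside, and that the variable is exploratory.

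Most of this stands. It settles what was probably intended, and it limits the consequence to one variable. It does not remove the conflict, because the SAP does not say which sentence governs. If the sentence is the excursion rule, it contradicts the general specification and leaves the level with no size rule of its own. If it is the level rule, it is misnamed and the excursion has no rule in its own subsection. Either reading needs an edit.

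The reply is also right that the amendment rationale should not be pressed. It explains a move from excursions to absolute values for the mixed meal test. It makes a premeal difference plausible, but it does not say that level and excursion must be kept apart in the CGM data.

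**Conclusion.** This is a minor internal inconsistency, worth correcting because following the endpoint's own subsection literally gives a wrong result. It affects one exploratory by-meal CGM endpoint. The primary objective, the five multiplicity-adjusted objectives, the alpha allocation and the sample size are untouched.

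Under the literal rule, the size of the error equals the premeal difference between arms, for unadjusted means over the same meals. The 5 to 10 mg/dL range is an illustration only. The error arises only if the general specification is overlooked.

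A reader might infer three stronger things, and the documents support none of them:

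- **That the SAP gives no derivation with a subtraction.** It does, through the general specification and the definition of G_i - G0.
- **That the sponsor chose to analyse the excursion as a level.** Two separate table rows and the general specification point to a merged sentence instead.
- **That no postprandial excursion is analysed from CGM.** The mean excursions and the iAUCs over 0 to 1, 2, 3 and 4 hours all subtract a premeal value.

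**What to change.** Replace the one sentence in Appendix 2 with two derivations:

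- Highest postprandial glucose level = max(G_i) over 0 to 4 hours after the start of the meal.
- Highest postprandial glucose excursion = max(G_i) - G0 over the same interval, with G0 as already defined for iAUC (the average over the -19 to 0 minute window).
- Both are truncated at the next meal event. The present sentence already carries this rule, and the rewrite must not lose it.

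The cost is one sentence of text and a check that the program matches it. The change needs no new data, definition or model, and it aligns the subsection with Table ITRO 6.5 and the rest of Appendix 2.
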